Results from clinical trial in young adult males with ASD: Sulforaphane was well tolerated and there were no significant toxic effects. SRS scores decreased by an average of -15 units in the sulforaphane group compared to -3 units in participants on placebo ($p=0.02$); considering the 4 drop-outs as non-responders, 31% (9/29) sulforaphane participants vs 0% placebo participants had a 25% decrease in total SRS score from baseline ($p=0.018$). The average change in total ABC score was -18 units in the sulforaphane group as compared to -1 units in the placebo group ($p=0.0001$), and after considering the 4 drop-outs as non-responders, 52% (15/29) sulforaphane participants vs. 13% (2/15) placebo participants had a 25% decrease in their total ABC score from the baseline ($p=0.02$). On the OACIS-I, participants on sulforaphane were much improved or very much improved on the following subdomains: social interaction, 41% (12/29) sulforaphane participants vs. 0% on placebo ($p=0.003$); aberrant/abnormal behavior, 48% (14/29) on sulforaphane vs. 6.7% (1/15) on placebo ($p=0.007$); repetitive/stereotypical behavior, 21% (6/29) on sulforaphane vs. 0% placebo ($p=0.08$); and verbal communication, 38% (11/29) on sulforaphane vs. 0% placebo ($p=0.008$). Seventeen of the 26 participants on sulforaphane who completed the trial were much or very much improved on at least one subdomain of the OACIS-I. Ninety-four percent (16) of those 17 on sulforaphane had a history of positive behavioral effects during febrile illness. In comparison, of the remaining 9 participants who were taking sulforaphane but were not much/very much improved on OACIS-I, only 55% (5/9) had a history of positive effects of febrile illness ($p=0.03$).

5) Inclusion and Exclusion Criteria*

- Inclusion criteria
 - Autism (ASD) diagnosis. Quantitative autism traits and severity for diagnosis of autism will be assessed by clinical judgment corroborated by the ADOS-G and DSM-V checklist of symptoms. ASD symptoms moderate to severe, based on ADOS criteria.
 - Age from 3 through 12 years.
- Exclusion criteria for subjects will include:
 - Absence of a parent or legal guardian and consent
 - Inability to speak/understand English language

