 - Seizure within 1 year of screening: This exclusion is based on the theoretical concern that cellular activation by sulforaphane might exacerbate seizures in patients with known seizure disorders. As previously noted in our previous trial of sulforaphane in young adult males, a seizure occurred in each of 2 participants: one during treatment (in a participant with a previously undisclosed seizure), the other 3 weeks after discontinuing sulforaphane.
 - Impaired renal function (serum creatinine > 1.2 mg/dl), impaired hepatic function (AST/ALT > 2x upper limit of normal), impaired thyroid function (TSH outside normal limits): This exclusion is based on a theoretical possibility of activation of underlying cellular metabolic abnormalities by sulforaphane. Current infection or treatment with antibiotics: this exclusion is to avoid complications of inter-current illness that may occur due to the clinical trial or obscure possible effects of sulforaphane.
 - Medications that may modify the course or testing of ASD parameters (e.g., prednisone): This exclusion is necessary in order not to interfere with or complicate effects of sulforaphane.
 - Chronic medical disorder (e.g., cardiovascular disease, stroke or diabetes) or major surgery within 3 months prior to enrollment: Serious medical illness in the child may be complicated by the clinical trial and make it difficult to discern a change in ASD associated with treatment.
 - Less than 3 years or more than 13 years of age: this age range was selected to cover the ages from usual diagnosis of ASD up to adolescence.
 - A diagnosis of autism spectrum disorder other than autism, for example, Asperger disorder, PDD-NOS, not consistent with moderate to severe autistic disorder, according to ADOS criteria.
 - Prisoners
 - Pregnant women

6) Study-Wide Number of Subjects*

NA

7) **Study-Wide Recruitment Methods***

NA

8) **Study Timelines***

Duration of intervention: 15 weeks in first (double blind, Phase 1), and 15 weeks in open-label (Phase2).

Prior to the main clinical trial, we will carry out a pilot study in 10 children with ASD, 6-12 years of age, who will receive sulforaphane, 2.2 micromoles/kg daily for 14 days (details below in “10: Procedures Involved (Study design)”).

The entire clinical trial is estimated to last 3 years. The following tables below depict our estimated timelines for study procedures and subject recruitment:

SPECIFIC AIMS/TASKS	TIMELINE (UMASS)	TIMELINE (JH)

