 - iv) Change in total SRS score (as well as subscales of social awareness, social cognition, social communication, social motivation and autistic mannerisms) from baseline
 - v) Determination of Nrf2 levels
 - vi) Determination of oxidative stress biomarkers
 - vii) Determination of Heat Shock Response biomarkers
 - viii) Determination of mitochondrial function biomarkers
 - ix) Determination of mTOR signaling pathway markers
 - x) Determination of immune function and inflammatory biomarkers
- c) *Safety endpoints*
- i) Liver function tests (ALT/AST)
 - ii) Renal function tests (serum creatinine)
 - iii) Thyroid function (TSH levels)
 - iv) Complete blood counts (WBC count, RBC count, platelet counts)
 - v) Urinalysis

Description of surveys used as the primary and secondary study endpoints:

1. **Ohio Autism Clinical Impressions Scale - Severity (OACIS-S)**^{27,28} is a 7 point, 10 domain scale that requires the clinician to rate the severity of the patient's ASD at the time of assessment, relative to the clinician's past experience with patients who have the same diagnosis. The questions are rated on a scale from 1 to 7 in the increasing order of severity, where “1” is normal (symptoms indistinguishable from typically developing children) and “7” is the most severe symptoms causing significant problems with individual functioning on a daily basis. The 10 items on the OACIS-S scale cover different domains of patients’ behavior, including global autism severity, social interaction, aberrant behavior, repetitive or ritualistic behaviors, verbal communication, non-verbal communication, hyperactivity/inattention, anxiety, sensory sensitivities and restricted/narrow interests. These are rated in a similar way to the NIMH CGI Severity scale, but it

- is focused on autism spectrum symptoms. This scale will be used to acquire clinician-assessed severity of autistic symptomatology in the study.

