A secondary analysis assessing proportion of participants in both groups who have responded to the study drug will be performed by Fisher's Exact test. This analysis will be done by categorizing the OACIS-I, SRS and ABC data. Participants will be considered as responders to study drug if they experience either of the following: they are much/very much improved (a score of 2 or less) on any subdomain of OACIS-I scale, their total ABC scores at 15 weeks decrease by at least 25% from baseline score, and their total SRS scores at 15 weeks decrease by at least 25% from their baseline score.

Biomarkers (testing mechanism of action of SFN) will be tested both as outcome variables in mixed model analyses and as predictors of differences in behavioral symptoms using the models described above for behavioral symptoms. Markers that both respond to sulforaphane treatment and predict differences in behavioral symptoms will be interpreted as possible mediators of any benefit from sulforaphane treatment. Safety of sulforaphane treatment will be assessed based on absolute rates of liver, thyroid and renal toxicity among participants treated with sulforaphane and based on comparison of the proportion of participants with such toxicities between the two treatment groups.

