Risk management and emergency response: Risks to subjects will be minimized by close follow-up and consideration of all reported symptoms and concerns of parents, guardians and caregivers. Regular examinations and laboratory testing of blood counts and serum chemistries, including liver function tests, renal function tests, and thyroid function tests will be performed at the screening visit, 7 week, 15 week, 22 week, 30 week and 36 week visits, and reviewed by the study team and Data Safety Monitoring Board. The PI or physician colleague will be on call 24/7 for any concerns of adverse events during the study. Risks of phlebotomy will be reduced by behavioral preparation, use of topical anesthetic and carried out by phlebotomists experienced in working with persons with autism. Protection of subjects will include confidential treatment of all health related information, and all research data will be coded, the reference codes to be maintained under lock and key by the PI and study coordinator at all times.

If lab signs of toxicity are found (AST/ALT > 2x upper limit of normal; serum creatinine > 1.2 mg/dl; TSH outside normal limits), the patient will discontinue study medication for 2 weeks before resuming the study medication, once lab values return to within study's acceptable limits. At the end of 2 weeks, we will do lab tests again. If at that time, lab tests are still not within study's acceptable limits (AST/ALT > 2x upper limit of normal; serum creatinine > 1.2 mg/dl; TSH outside normal limits), subjects will discontinue permanently the study medication (though they will still continue to be followed-up in the study). Lab tests are required at screening, 7-week, 15-week, 22 week, 30 week and closeout visits: Hematology and complete metabolic profile (including liver, kidney, thyroid function tests); urinalysis for protein and hemoglobin. Possible clinical side effects of sulforaphane will be monitored, including: GI disturbances (flatulence, soft stool, and large bowel movement), and frequent urination⁶³. Staff members will be available 24/7 for emergencies. Maximum amount of blood drawn at any stage during this study will not exceed 2 ml/kg body weight; also we will not exceed the minimal risk requirements of 3ml/kg in an 8 week period.

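### Laboratory safety is analysed only as rates of undefined toxicities; under the only thresholds given, a doubled creatinine can go uncounted while one stray TSH value counts

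*Combined protocol and SAP*

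**What the plan says.** Section 12 (Data Management, Statistical Analysis) assesses safety in two ways. The first is "based on absolute rates of liver, thyroid and renal toxicity among participants treated with sulforaphane". The second is "based on comparison of the proportion of participants with such toxicities between the two treatment groups". It sets no threshold for any of the three toxicities and refers to no other section for one.

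Section 9 lists the safety endpoints as the tests themselves, for example "Renal function tests (serum creatinine", also without cut-offs.

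Section 13 (Risk management and emergency response) is where limits are called signs of toxicity: "If lab signs of toxicity are found (AST/ALT > 2x upper limit of normal; serum creatinine > 1.2 mg/dl; TSH outside normal limits". There they act as a trigger for pausing study drug. The same limits decide entry in Section 5: "Impaired renal function (serum creatinine > 1.2 mg/dl" and "impaired thyroid function (TSH outside normal limits" are exclusions. They apply to everyone in the range "Age from 3 through 12 years", with no age bands.

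Each child has a screening value for all these tests. The plan uses it for eligibility but not as a baseline for a laboratory analysis.

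**The concern.** Aim 2 is safety in children, and Section 15 says that no study has been designed explicitly to test that. The laboratory part of the answer rests on counts of children who cross a limit. If the Section 13 limits are the ones counted, two difficulties follow.

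- **Creatinine.** The other limits are expressed relative to a reference range. Creatinine is one absolute value from age 3 to age 12, with no change-from-baseline criterion. A large relative rise in a child with a low starting value would not enter the renal toxicity rate.
- **TSH.** A single value on either side of normal is enough. No size, direction, change from baseline or persistence is asked for. Repeated testing of healthy children will therefore produce some thyroid toxicities by chance.

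At stake is how two possible statements in the report would be read: that no renal toxicity occurred, and that a given percentage of treated children had thyroid toxicity.

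**Working it through.** **The plan's own figure.** The only number attached to toxicity detection is in Section 12 (Power Calculations): 80% power to see one or more toxicities at a true rate of 5.3%. The formula is 1 − (1 − 0.053)^n.

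- n = 25 (one Phase 1 arm): 74.4%.
- n = 50 (all exposed by Phase 2): 93.4%.
- 80% requires n = ln(0.2)/ln(0.947) = 29.6, a number of treated children that the plan does not give.

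The figure does not reproduce. That is a separate matter; 5.3% is used below only as a yardstick.

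**Creatinine.** The input is the 1.2 mg/dl limit (Section 13). Baselines are assumptions. The fold rise needed to reach the limit is 1.2/baseline:

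| Baseline (mg/dl) | 0.3 | 0.4 | 0.5 | 0.6 | 0.7 | 0.8 |
|---|---|---|---|---|---|---|
| Fold rise | 4.0 | 3.0 | 2.4 | 2.0 | 1.7 | 1.5 |

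Below 0.6 a doubling goes uncounted, and below 0.4 a tripling does. Above 0.6, any doubling is counted.

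**TSH.** From the documents: two post-screening tests in Phase 1 (weeks 7 and 15), four by week 30 (Section 10, Monitoring for safety), screening value within limits (Section 5), and 25 children per arm (Section 12). Section 13 adds a closeout test; this does not affect the week 7 and 15 figures.

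Assumptions: a stable healthy child, normally distributed values with equal within-child correlation ρ, and normal limits that hold the central 95% of healthy children. Model: X_j = √ρ·U + √(1 − ρ)·e_j, flagged if |X_j| > 1.96, conditional on |X_0| ≤ 1.96 at screening. Results by simulation:

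| ρ | Any flag, 2 tests | Expected in 25 | P(at least 1 of 25) | Any flag, 4 tests |
|---|---|---|---|---|
| 0 | 9.7% | 2.4 | 92% | 18.6% |
| 0.5 | 8.0% | 2.0 | 87% | 14.0% |
| 0.7 | 6.2% | 1.6 | 80% | 10.4% |
| 0.9 | 3.5% | 0.9 | 59% | 5.4% |
| 0.95 | 2.5% | 0.6 | 47% | 3.7% |

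The ρ = 0 row can be checked in closed form: 1 − 0.95² = 9.75% and 1 − 0.95⁴ = 18.5%.

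With limits that hold 99% of healthy children, the two-test figure is 2.0% at ρ = 0 and 0.6% at ρ = 0.95. The chance of at least one flag among 25 is then 1 − 0.98^25 = 40% and 1 − 0.994^25 = 14%.

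**Effect on the between-arm comparison.** Chance flags are equally likely in both arms, so there is no bias. For Fisher's exact test with 25 per arm and a true 30-point excess, power is 81% with no background, 70% with 5% background and 59% with 10%.

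**Check against the earlier trial.** Section 15 reports that no laboratory result was out of range in 40 participants. Under the 95% model, the chance of that is (1 − p)^40, with p the probability of any flag over three or four later tests: 0.03% to 0.9% at ρ = 0 to 0.5, 1% to 3% at 0.7, 11% to 15% at 0.9, and 22% to 28% at 0.95.

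**The case against.** The strongest reply is that Section 12 already contains the concurrent control. Its second analysis compares proportions between the two groups, and background TSH flags fall on both arms alike. This stands: the comparison is not biased. It does not rescue the first analysis, an absolute rate in treated children, because everyone is on sulforaphane in Phase 2 and no placebo rate exists for that period. Section 12 also says that the trial is not powered to compare safety rates for a relevant non-inferiority threshold.

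Second, the earlier trial saw no out-of-range result. If TSH was among its tests, high within-person correlation and the low end of the range are more plausible. Section 15 does not say that it was, and those participants were aged 13 to 30. At ρ = 0.95 with 95% limits, the chance of at least one flag in an arm of 25 is still 47%.

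Third, the Section 13 limits are written as pause triggers, and reading them as endpoint definitions is an inference. This also stands. If they are not the definitions, the toxicity rates have none.

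Fourth, Section 13 provides urinalysis, DSMB review and a two-week retest. These help monitoring, and the retest decides whether study drug is stopped. Nothing in Section 12 says that only confirmed abnormalities count, or brings urinalysis into the renal rate.

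A reader might infer that all three limits are wrongly scaled for children. The documents do not support that: AST/ALT and TSH are tied to reference limits, and nothing says that those limits are not age-specific. For TSH the weakness is low specificity under repeated testing, which would apply at any age.

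**Conclusion.** The point holds as a modest, cheap improvement to the safety analysis. Section 12 leaves its toxicities undefined and plans no analysis of laboratory change from baseline.

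Under the Section 13 limits, a doubling of creatinine is missed for baselines below 0.6 mg/dl and a tripling for those below 0.4. How often that could arise depends on baselines that the documents do not give. It would go too far to say that the limit generally misses multi-fold rises.

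For TSH, the chance that a stable healthy child is flagged in Phase 1 is about 2.5% to 10% with 95% limits and 0.6% to 2% with 99% limits, for ρ from 0.95 to 0. The 95% range spans the plan's 5.3% yardstick, so one or two thyroid events in the treated arm would say little. This is a probability under stated assumptions; it does not show that healthy children will be counted.

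The absolute thyroid rate should not be read without a placebo rate beside it. Nothing here judges whether the limits suit their clinical use.

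**What to change.** Change the safety paragraph of Section 12 only:

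1. State that the liver, thyroid and renal toxicity counts use the Section 13 limits, say whether a first or a confirmed abnormality counts, and label the counts descriptive.
2. Add creatinine, TSH, ALT and AST as the ratio to the child's own screening value at weeks 7 and 15, sulforaphane versus placebo, with 95% CI.
3. Add shift tables from screening against the laboratory's reference limits, naming the ranges used.
4. Show absolute thyroid and renal rates beside the Phase 1 placebo rate.

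All these values are already collected. The cost is some wording and one extra table, with no new tests and no change to care.

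No clinical cut-off, pause rule or stopping rule is proposed. The clinical team and DSMB do need to reconcile two texts. The visit descriptions in Section 10 and the risk-management text in Section 13 pause study drug on a laboratory result alone. The laboratory items in the Section 13 list of pause criteria also require a reported serious side effect.
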